5.1 Background Characteristics

5.1.1 Patient disposition

Enrollment and disposition data will be presented for each patient in data listings and summarized by frequency tables.

Patient enrollment eligibility and inclusion and exclusion criteria deviations will be presented in data listings.

5.1.2 Protocol deviations

All protocol deviations reported by the clinical team will be presented in a data listing sorted by center, category and patient.

Protocol deviations captured in the database such as:

- Non-adherence to study inclusion and exclusion criteria
- Failure to obtain informed consent prior to beginning the study
- Wrong study treatment received, or an incorrect dose
- Other data deviations as observed upon review of the data

Major protocol deviations are defined as those that could potentially bias either the PK or safety conclusions of the study. All other protocol deviations are defined as minor protocol deviations. Protocol deviations will be reviewed prior to database lock and classified as major or minor based on medical review.

5.2 Demographics and Other Baseline Characteristics

5.2.1 Demographics

Descriptive statistics of baseline data will be presented for cohort 1. The following baseline demographic data will be presented:

- Post-natal Age [days] at Day 1 / Gestational Age [weeks]
 - Continuous summary
- Sex
 - Categorical summary (Male, Female)
- Race
 - Categorical summary (White, Black or African American, Asian, American Indian or Alaska Native, Native Hawaiian or Other Pacific Islander, Other)
- Height [cm]
 - Continuous summary
- Weight [g]
 - Continuous summary

5.2.2 Medical history

Medical history of diseases will be summarized in tables by SOC, and PT, including number of subjects and percentage relative to the numbers of subjects in the corresponding study groups.

5.3 Prior and Concomitant Medications

Data concerning concomitant medications and procedures will be collected throughout the study. These data will be obtained at scheduled or unscheduled study visits, based on information provided by the subject's parent or legal guardian.

The coding of medications will be performed using the WHODRUG enhanced dictionary and partial start and/or end dates will be imputed as described in section 4.3.

Medications will be classified based on the observed or imputed start dates into:

- A medication is classified as prior if it started and stopped before the reference start date of the subject.
- A medication is classified as concomitant medication if it started on or after the reference start date of the subject.
- A medication is classified as ongoing if it started before the reference start date of the subject and is still ongoing after the reference start date.

Prior medications, concomitant and ongoing medications will be presented in a listing.

Concomitant and ongoing medications will be summarized in tables by Anatomical Therapeutic Chemical (ATC) level 4 code, and Preferred Term (PT), including number of subjects and percentage relative to the numbers of subjects in the corresponding study groups.

5.4 Treatment Compliance and Exposure

Exposure to study drug will be summarized. The total dose taken will be presented.

5.4.1.1 Pharmacokinetic analysis

Plasma concentrations at each time point of measurement will be evaluated by descriptive statistics, including arithmetic mean, standard deviation (SD), minimum, maximum, and median. Actual sampling times will be used to calculate PK parameters. If $\leq 50\%$ of the values at a given time point are BLQ, these values will be set to zero for mean value calculation. If more than 50% of the values at a given time point are BLQ, no mean value will be calculated. Mean plasma concentration profiles of cohort 1 will be generated according to these criteria.

For PK evaluation, BLQ-values at infusion start will be set to zero, BLQ-values at the end of the sampling period will be disregarded for PK assessment. Single BLQ values during blood sampling will be taken as 'missing values', if the following sample(s) show a concentration above the BLQ value.

5.5 Safety Analysis

Definitions of adverse events (AEs) and serious adverse events (SAEs) as well as information on

reporting procedures for AEs/SAEs are provided in the clinical trial protocol. AEs will be coded using the Medical Dictionary for Regulatory Activities (MedDRA version 20.1) and partial start and/or end dates will be imputed as described in section 4.3.

Frequency tables summarizing the incidence and observed number of treatment-emergent adverse events by treatment and by System Organ Class and Preferred Term will be prepared with 3 levels of detail:

- All adverse events
- Adverse events by severity (mild/moderate/severe)
- Adverse events by relationship to study drug (not related/related)

An adverse event is classified as treatment emergent if the following conditions are met:

- Start date and end date of adverse event is missing.
- Start date is missing but end date is not before reference start date of treatment
- Start date is missing but end date is after reference start date
- Start date is on or after reference start date.

Summary tables for all adverse events and for adverse events by severity will be presented for cohort 1.

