7 SUBJECT SAFETY

7.1 Adverse events

7.1.1 Definition of adverse events

An AE is any adverse change from the subject's baseline (pre-therapy) medical condition which occurs during the course of a clinical study after test medication has been given, whether considered related to treatment or not. Treatment includes all study drugs administered during the course of the study. Events involving exacerbations or worsening of pre-existing illnesses should be recorded as AEs.

A treatment-emergent AE in this study is defined as any AE occurring between first administration of study drug and the follow-up visit at study Day 7±3. If the last scheduled study visit occurs later than 10 days after stopping the treatment, any AE occurring after Day 10 will be considered non-treatment-emergent unless reassigned based on a medical review conducted by the sponsor prior to database lock.

Adverse medical occurrences that appear between the provision of informed consent and first drug administration will be entered into the Medical History section of the eCRF.

If possible, a diagnosis should be documented rather than signs and symptoms. All AEs should be recorded in the English language.

Abnormal laboratory values or test results constitute AEs only if they induce clinical signs or symptoms, are considered clinically significant, or require therapy. These events are to be entered into the Adverse Events section of the eCRF under the signs, symptoms or diagnoses associated with them.

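### SAP 5.5 gives treatment-emergence no end point, while Protocol 7.1.1 ends it at the follow-up visit, so a few late events get a different default classification

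*SAP*

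**What the plan says.** Protocol 7.1.1 defines a treatment-emergent event as "any AE occurring between first administration of study drug and the follow-up visit at study Day 7±3". A second sentence deals with late visits. It begins "If the last scheduled study visit occurs later than 10 days after stopping the treatment" and continues that "any AE occurring after Day 10 will be considered non-treatment-emergent unless reassigned based on a medical review", which the sponsor must carry out before database lock. So the protocol has an end point, a conditional Day 10 default and a way to override that default.

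SAP 5.5 opens by sending the reader to the protocol for "Definitions of adverse events (AEs) and serious adverse events (SAEs) as well as information on" reporting procedures. It then states its own rule: "An adverse event is classified as treatment emergent if the following conditions are met", followed by four conditions. Three deal with missing start dates, for example "Start date is missing but end date is not before reference start date of treatment". The fourth, for a known onset, is "Start date is on or after reference start date". All four either concern missing dates or look back to the reference start date. None mentions the follow-up visit, Day 10 or the medical review. The frequency tables by system organ class and preferred term, by severity and by relationship are built on events that pass this rule.

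**The concern.** The secondary objective is safety and tolerability, and the treatment-emergent tables are its main summary output. A programmer who follows SAP 5.5 will count some events that the protocol excludes by default, and the SAP does not announce or justify a departure. These infants are already being treated for infection or are at risk of it, and each gets one infusion. An open-ended window can therefore attribute a late background event to the emergent period after a single dose. In a cohort of 15, even one reclassified infant shows in a percentage.

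**Working it through.** No sample size, power or test figure is involved. The check is to apply both rules to the same events and then size one reclassification.

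**Inputs**
- The two rules: SAP 5.5 and Protocol 7.1.1.
- Collection period: Protocol 5.2.3.1 records AEs up to the final follow-up assessment. Protocol 7.2.2 extends SAE reporting to the actual date of a late visit and still wants drug-related SAEs reported after the last visit.
- Day numbering (SAP 4.2): study day = date − dosing date + 1, so dosing is Day 1.
- Number of infants: 15 planned per cohort (SAP 2.3.1), and only Cohort 1 was completed (SAP 2.3.1.1). That 15 is also the safety population is an assumption.

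**Step 1. Same events, both rules**

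| Case | Visit | Event | Protocol 7.1.1 | SAP 5.5 |
|---|---|---|---|---|
| a | Day 7 | AE, onset Day 5 | emergent | emergent |
| b | Day 14 | AE, onset Day 12 | not emergent by default; review may reassign | emergent |
| c | Day 5 | related SAE, onset Day 8 | outside the window | emergent |
| d | Day 7 | related SAE, onset Day 20 | outside the window | emergent |

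In case b the visit is 14 − 1 = 13 days after dosing, so the late-visit sentence applies. Cases c and d assume that an SAE reported after the last visit reaches the dataset behind the tables; the protocol says it should be reported but not where it is stored. In both, the visit was not late, so the review clause as worded does not come into play. For an infant seen on schedule, with only routinely collected events, the two rules agree.

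**Step 2. The protocol's two anchors**

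Ten days after an infusion that stops on Day 1 is Day 10 + 1 = Day 11, whereas Day 10 is 10 − 1 = 9 days after dosing. The protocol synopsis gives a 6 ± 3-day follow-up, which matches Day 7±3 only if dosing is Day 1 (7 − 1 = 6). A visit on Day 11 is exactly 10 days after stopping, so it does not trigger the late-visit sentence, yet it lies outside Days 4 to 10. An AE with onset on Day 11 is then not clearly assigned by either sentence.

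**Step 3. Imputed dates once an end point is added**

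SAP 4.3 sets a missing day to the 15th when the month is not the month of treatment. Take dosing on 30 March and an onset recorded only as April. The imputed onset is 15 April, 16 days later, which is Day 17. The true onset could be as early as 1 April, 2 days later, which is Day 3. A bare Day 10 cutoff would make this event non-emergent on the imputation alone. SAP 4.3 allows case-by-case handling if the imputed date conflicts with other data, but with a late visit no conflict need appear.

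**Step 4. Size**

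One infant whose only event in a table row is reclassified changes that row by 1/15 = 6.7 percentage points. If the infant has another qualifying event in the row, the change is 0. Protocol 4.4 allows replacement after an incomplete infusion, and the replaced infant stays in the safety population (SAP 3.2). With 16 or 17 infants the maximum is 1/16 = 6.3 or 1/17 = 5.9 points.

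**The case against.** The strongest reply is that the SAP already defers to the protocol. Its opening sentence points to the protocol's adverse event definitions, and the section of that name, 7.1.1, holds the window. On this view the four conditions are only date logic beneath the protocol's definition. This is arguable but does not settle the matter. The pointer names AE and SAE definitions and reporting, and the SAP then gives a complete classification rule of its own. Section 5 relies on double programming, and two programmers could both follow that rule without opening the protocol.

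The second reply is about scale, and it stands. Routine collection stops at the follow-up visit, nothing in the documents shows that any visit was late, there is no comparator or test, all individual data are listed, and the error is over-inclusion. A wider window can also be defended as conservative, but then the SAP should say that it departs from the protocol and why.

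Two stronger readings are tempting.
- A reader might infer that no event can ever qualify, because the conditions cannot all hold together. The first and fourth do exclude each other, and the third is contained in the second. Only an any-of reading works, so this is a wording slip with no analytic consequence.
- A reader might infer that the protocol makes every event after Day 10 non-emergent. It does not: that sentence applies only when the last visit is late, and medical review can reverse the result.

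**Conclusion.** The inconsistency is real and small. SAP 5.5 as written and Protocol 7.1.1 give different default classifications for events captured at a late visit and for drug-related SAEs reported after the last visit, and for nothing else that is routinely collected. The effect is at most 6.7 percentage points per infant per table row, assuming 15 infants and no other qualifying event in the row. The documents do not show how many such events exist, and probably there are few.

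It would go too far to conclude that the safety tables as a whole are unreliable, or that each reclassified infant necessarily moves an incidence by 6.7 points. It would also be wrong to think that a simple cutoff at the earlier of the visit or Day 10 costs nothing. That cutoff would drop a related SAE such as case c, and the protocol's review clause, which covers only events after Day 10, would not restore it. This is a low-priority correction, worth making because it is cheap.

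**What to change.** Change SAP 5.5 only; the protocol need not be amended.

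1. State that an event is treatment-emergent if ANY of the listed conditions holds.
2. Apply the end point in Protocol 7.1.1, including its condition for late visits and the sponsor's reassignment step before database lock.
3. State in the SAP's day numbering (Day 1 = dosing) how the 10-days-after-stopping trigger and the Day 10 limit are reconciled, so that a Day 11 visit or event has a defined class.
4. State that an imputed date alone does not make an event non-emergent.
5. Show drug-related SAEs with onset after the follow-up visit in the safety tables or in a separate display, so that the cutoff does not remove them.

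The cost is a few lines of SAP text and the matching programming. The small downside is that late background events leave the main table and appear only in the listings.

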5.6 Clinical Laboratory Evaluations

The laboratory parameters collected per protocol will be described using summary statistics and shift tables. Summary statistics will be presented for absolute values and absolute change from baseline.

Reference ranges (low/high, negative/positive, normal/abnormal) will be presented in shift tables to show shifts from baseline values at the different time points.

5.7 Vital Signs

The actual and change from baseline values of the following vital signs will be summarized using descriptive statistics

- Systolic blood pressure
- Diastolic blood pressure
- Pulse rate
- Temperature
- Respiration rate

In addition marked reference changes from baseline will be presented for vital signs. Marked reference change will be defined as follow:

- Diastolic Blood Pressure: <60 or >100 mmHg.
- Systolic Blood Pressure: <80 or >180 mmHg.

- Pulse: <40 or >120 beats/min.
- Temperature: <36.0 or >38.5 degree Celsius.

